2.2.1.2 Malignant Melanoma

Melanoma is 1 of the most common cancers in the United States, and is the most morbid malignancy of the skin, accounting for up to 75% of skin cancer-related deaths. While early melanoma is a localized disease, and is most often curable by surgical resection before metastatic spread, disseminated melanoma is a difficult disease to treat effectively.

Melanoma is a highly immunogenic tumor due to somatic mutations in the genomes of melanoma cells caused by ultraviolet radiation. These somatic mutations cause neoantigens in the tumor that can be recognized by the immune system, enabling a T-cell mediated antitumor immune response. Thus, immunotherapy can be an effective treatment for melanoma. Recent advances with CPIs have increased the 3-year survival rate of advanced melanoma to as high as 58%,³ but CR rates are generally low, and recurrent and refractory disease remains an unmet medical need. High-dose IL-2 can also potentiate T-cell mediated antitumor responses in melanoma, with an objective response rate (ORR) of 16%, including a CR rate of 6%.⁴ As described above, the severe toxicity associated with IL-2 therapy has limited its use to patients with good organ function who are being closely monitored by experienced clinicians in specialized medical centers.

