2.3 Benefit/Risk Assessment

Potential risks for the planned NL201-101 first-in-human clinical study comprise cytokine release syndrome, flu like symptoms, cardiac toxicity, and auto-immunity. Considering the high unmet medical need in the targeted patient population and that patients do not forego any established and effective standard therapy, the risk/benefit ratio of applying an engineered IL-2 mimetic with potential for durable responses that is safer than IL-2 is considered justified by the Sponsor. To further lower the safety risks for patients in the NL201-101 study, risk mitigation measures have been implemented at multiple levels in the design of the clinical study. These include dose escalation/de-escalation, prophylactic measures, steps that allow for early diagnosis and/or aggressive clinical management of safety events, and a Data Monitoring Committee (DMC).

More detailed information about the known and expected benefits and risks and reasonably expected adverse events (AEs) of NL-201 may be found in the Investigator's Brochure.

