5 STUDY POPULATION

Before any study-specific activities/procedures, the appropriate written informed consent must be obtained (see Section 10.1.3). Patients must meet all enrollment criteria to be eligible for this study.

Part 1 target population: Adult patients with measurable advanced and incurable solid tumors who have failed all lines of treatment, including CPIs if indicated.

Part 2 target population: Adult patients with pathologically proven diagnosis of the target disease indications, (1) malignant melanoma and (2) RCC, who have advanced and incurable disease and have failed at least 1 line of treatment, including CPIs.

Part 3 target population: Adult patients with histologically-confirmed solid tumors who have received ≥ 1 prior line of therapy for advanced or metastatic disease.

Part 4 target population: Adult patients with pathologically proven diagnosis of the target disease indications, (1) ICI naïve malignant melanoma and (2) ICI naïve RCC, and (3) patients with

NSCLC, melanoma, or HNSCC who have received prior treatment with pembrolizumab achieving a best response of SD.

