- e. Coagulation (specimens must be collected within 10 days prior to the start of study treatment): international normalized ratio (INR) OR prothrombin time (PT) $\leq 1.5 \times$ ULN unless participant is receiving anticoagulant therapy as long as PT or partial thromboplastin time (aPTT) is within therapeutic range of intended use of anticoagulants
6. At least 6 weeks from any prior nitrosurea or mitomycin C therapy; at least 4 weeks from any other prior chemotherapy or CPI; at least 2 weeks from any kinase inhibitor.
7. Women are not pregnant or breastfeeding and 1 of the following conditions applies:
 - a. Is a woman of non-childbearing potential as defined in [Section 10.4](#)
 - b. Is a woman of childbearing potential (WOCBP) and using a contraceptive method that is highly effective, with a failure rate of $< 1\%$ (as described in [Section 10.4](#)) during the study treatment period and for at least 60 days after the last dose of NL-201 (Parts 3 and 4 only: 120 days after the last dose of study treatment). The Investigator should evaluate the potential for contraceptive method failure (eg, noncompliance, recently initiated) in relationship to the first dose of study drug.
8. A WOCBP must have a negative highly sensitive pregnancy test (serum or urine) at screening.
9. Men are eligible to participate if they agree to the following during the study drug period and for at least 90 days after the last dose of NL-201 (Parts 3 and 4 only: 120 days after the last dose of pembrolizumab):
 - a. Refrain from donating sperm
 - b. For men with partners of childbearing potential or partners who are pregnant or breastfeeding: Use a male condom and should also be advised of the benefit for a female partner to use a highly effective method of contraception as a condom may break or leak when having sexual intercourse with a woman of childbearing potential who is not currently pregnant.

Part 1 Only

10. Patients with any relapsed or refractory advanced solid tumor, other than prostate cancer, who have progressed, not tolerated or are ineligible for all approved non-IL-2-based lines of therapy.

Parts 2 and 4 Only

11. Patients with a diagnosed target disease indication that has failed at least 1 line of systemic therapy.

Parts 3 and 4 Only

12. Part 3 only: Patients with histologically-confirmed solid tumors who have received ≥ 1 prior line of therapy for advanced or metastatic disease.

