9.2 Sample Size Determination

In Part 1, 2 NL-201 monotherapy dosing schedules (IV Schedule A, IV Schedule B) will be evaluated with the goal being to determine the MTD of each schedule. The MTD is defined as the highest dose for which the probability of a patient experiencing a DLT with NL-201 is $\leq 33\%$. Based on the totality of data arising in Part 1, the DMC will determine a RP2D and treatment schedule of NL-201 for Part 2 that will not exceed the MTD.

Dose escalation in Part 1 will be guided by an mTPI design with up to approximately 50 enrolled per schedule as depicted in [Figure 5](#). This design and number of patients per schedule provides a high likelihood of correctly identifying the MTD with approximately one half of the patients (ie, approximately $n = 15$) being exposed to the MTD, very few being exposed to lower, less effective doses and relatively few being exposed to the MTD+1 dose.

In addition, there will be backfill cohorts (up to approximately 12 patients in total), at certain DMC-cleared dose levels and schedules, to collect, pharmacokinetic, pharmacodynamic and response data in certain tumor types or to explore additional pre-medication regimens (eg. steroids). The decision to enroll patients into backfill cohorts and to define the patients to be enrolled will be made by the Sponsor.

Note: “Enrolled” means any patient that has met all of the study inclusion and exclusion criteria and is eligible to receive study drug.

In Part 2, an expansion cohort study will evaluate safety and estimate antitumor activity of NL-201 as a monotherapy at the RP2D in 2 cohorts of patients: (1) melanoma and (2) RCC. A Simon’s 2-stage design will be used for each cohort independently to test the null hypothesis that the true monotherapy response rate is $\leq 2.5\%$ vs the alternative that the true response rate is $\geq 15\%$. In the first stage, 18 patients will be evaluated. If 0/18 objective responses are seen, recruitment to the cohort will be stopped for futility. Otherwise, a further 12 patients will be evaluated for a total of 30 patients. This design provides 80% power and a Type I error rate of 0.031 under the stated null and alternative hypotheses.

In Part 3, with the mTPI study design, the exact number of patients needed to complete the dose escalation is unknown because it depends on the number of cohorts required to reach MTD and the number of patients in each cohort. Dose escalation will be conducted in up to 42 adult

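### Part 2's numbered eligibility criteria do not carry Section 5's checkpoint-inhibitor condition, so a positive Part 2 test might not show activity in the CPI-failed population that Section 5 names

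*Combined protocol and SAP*

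**What the plan says.** Section 5 (Study Population) describes Part 2 as adults with advanced, incurable melanoma or RCC who "have failed at least 1 line of treatment, including CPIs". The Part 1 description in the same section qualifies its CPI condition with an if-indicated clause. The Part 2 description has no such clause. For Part 4, Section 5 names two cohorts that must be naive to checkpoint inhibitors (melanoma and RCC) and a third with prior pembrolizumab.

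Section 5.1, criterion 11, under a heading that covers Parts 2 and 4, reads: "Patients with a diagnosed target disease indication that has failed at least 1 line of systemic therapy".

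Section 9.2 applies a Simon two-stage design to each Part 2 cohort, with a null response rate of at most 2.5% and an alternative of at least 15%. Stage 1 takes 18 patients and has this futility rule: "If 0/18 objective responses are seen, recruitment to the cohort will be stopped for futility". A cohort that passes adds 12 more, which makes 30. The section reports 80% power and a type I error of 0.031. It does not give the number of responses needed for success at the end, or a source for the 2.5%.

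Section 9.4.3 analyses Part 2 response by expansion cohort with an exact binomial interval. It plans no stratification, cap or subgroup by prior CPI.

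**The concern.** Section 9.2 counts a patient as enrolled once the inclusion and exclusion criteria are met, and Section 8 also makes those criteria the gate. A site working through Section 5.1 could therefore enrol, for example, an RCC patient who failed a kinase inhibitor and never received a CPI. Section 5 places that patient outside the Part 2 population.

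Part 2 holds the only formal hypothesis test in the study (Section 9.1). If CPI-naive patients respond to NL-201 more often than CPI-failed patients, a cohort could reject its null largely because of who was enrolled. With no planned split by prior CPI, the result would not show whether the drug is active in the patients whom Section 5 describes. The decision at stake is whether to carry monotherapy forward in a CPI-failed population, on up to 60 patients across the two cohorts.

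**Working it through.** **Does anything else close the gap?**

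- Criterion 11 applies to Part 4 as well, where two cohorts must be CPI-naive. It cannot be read as silently requiring CPI failure.
- Criterion 6 sets a washout if a CPI was given. It does not require that one was given.
- Criteria 10 and 12 to 14 apply to Part 1, Part 3 or Part 4 only.
- No exclusion in Section 5.2 removes CPI-naive patients from Part 2.
- The Part 2 descriptions in Sections 1.1, 4.1 and 9.2 name melanoma and RCC without a CPI condition.

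Nothing in the numbered criteria closes it.

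**Inputs from Section 9.2:** 18 patients in stage 1, stop at 0 responses, 12 more for a total of 30, null 2.5%, alternative 15%.

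**Assumptions, because the documents give no value:** success at 3 or more responses of 30; a true rate of 2.5% in CPI-failed patients; the CPI-naive share f; the response rate pN in CPI-naive patients.

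**Formula.** For a true response rate p:

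P(success) = Σ over x = 1 to 18 of C(18, x) p^x (1 − p)^(18 − x) × P[Bin(12, p) ≥ 3 − x]

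For a mixed cohort, p = f × pN + (1 − f) × 0.025.

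**The plan's own figures first.** At p = 0.025:

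- 1 response in stage 1, then at least 2 of 12: 0.2926 × 0.0349 = 0.0102
- 2 responses in stage 1, then at least 1 of 12: 0.0638 × 0.2620 = 0.0167
- 3 or more responses in stage 1: 0.0096
- Sum: 0.0366. At p = 0.15 the same formula gives 0.834.

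A cut-off of 2 gives 0.150 and 0.922, and a cut-off of 4 gives 0.006 and 0.673. None of these matches the stated 0.031 with 80% power. A total of 18 + 10 = 28 with 3 or more responses does match (0.0311 and 0.803). That mismatch is a separate matter. Here it means that the cut-off of 3 is inferred.

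**Effect of patient mix** (18 + 12 = 30, success at 3 or more). Example: f = 0.3 and pN = 0.15 give p = 0.3 × 0.15 + 0.7 × 0.025 = 0.0625, and P(success) = 0.277.

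| Assumed rate in CPI-naive patients | No naive patients | 10% naive | 20% naive | 30% naive |
|---|---|---|---|---|
| 2.5% | 0.037 | 0.037 | 0.037 | 0.037 |
| 5% | 0.037 | 0.046 | 0.057 | 0.069 |
| 10% | 0.037 | 0.069 | 0.112 | 0.162 |
| 15% | 0.037 | 0.097 | 0.180 | 0.277 |
| 25% | 0.037 | 0.162 | 0.339 | 0.518 |

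**Two checks.** With the 28-patient version that matches the stated error rate, the 15% row becomes 0.031, 0.084, 0.158 and 0.247, which is the same pattern. With fixed numbers of naive patients spread over the two stages instead of a random mix, and a naive rate of 15%, 5 or 10 naive patients of 30 give 0.147 and 0.313.

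**The case against.** A reader might infer that patient mix inflates the type I error. The documents do not support that. The stated null concerns the response rate in each cohort, and Sections 4.1 and 9.2 define the cohorts by disease alone. At a mixed true rate of, say, 6.25% that null is false, so 0.277 is the chance of detecting a small real effect. Responses in CPI-naive patients would be real responses to NL-201. Nor do the documents say that 2.5% is a CPI-failed benchmark; that link comes only from the Section 5 description. This objection stands, and the point is therefore confined to what a positive result would show about CPI-failed patients.

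The naive share and naive response rate are also ungrounded. The one related figure, the 16% response rate for high-dose IL-2 in melanoma (Section 2.2.1.2), concerns another drug, is not labelled CPI-naive and does not cover RCC. Few naive patients may enrol: Section 2.1 places CPIs in the standard of care for both diseases, Section 2.3 says that "patients do not forego any established and effective standard therapy", and Part 4 has its own CPI-naive cohorts. That limits the likely size. But these statements are rationale, and no Part 2 criterion enforces them.

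Sites might apply the Section 5 description alongside the list, since the CPI-naive condition for Part 4 also appears only in such descriptions. The Part 2 phrase could also mean that a CPI counts as a line of therapy. Both readings are possible. The second fits poorly beside the qualified Part 1 wording, and two defensible readings of who may enter a test are themselves a reason to settle the text.

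Finally, it would be too strong to call the result uninterpretable. A full SAP is still to be written, and response by prior CPI could be reported from it.

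**Conclusion.** The inconsistency is in the text. Section 5 sets a CPI condition for Part 2, criterion 11 does not carry it, and no other numbered criterion does. CPI-naive patients can therefore enter the Part 2 test, and a rejected null might not show activity in the population that Section 5 names.

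The size is conditional. It rests on a 2.5% rate in CPI-failed patients, an inferred cut-off of 3 of 30, and an assumed naive share and naive response rate. The chance of a positive result driven by mix is 3.7% with no naive patients. With a 10% to 30% naive share it is 4.6% to 6.9% if naive patients respond at 5%, 6.9% to 16% at 10%, 9.7% to 28% at 15%, and 16% to 52% at 25%. If naive patients also respond at 2.5%, mix changes nothing. The documents do not show where in this range the trial would fall. This should be settled before Part 2 enrols, because it decides who enters the test and which population a positive result describes.

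**What to change.** Reconcile Section 5 and criterion 11 in one of two ways.

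1. If Section 5 states the intent, split criterion 11. Give Part 2 its own criterion with the Section 5 condition on prior CPI, and leave the Part 4 wording unchanged so that its CPI-naive cohorts are not affected.
2. If CPI-naive patients are intended in Part 2, revise the Section 5 description, justify the 2.5% null for the mixed population in Section 9, and plan Part 2 response by prior CPI status in the SAP.

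The first option costs one phrase in Section 5.1 and a slightly narrower recruitment pool, limited to patients whom Section 5 already places outside the population. The second costs a short justification and one extra summary for each cohort.

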5.2 Exclusion Criteria

Patients are excluded from the study if any of the following criteria apply:

Medical Conditions

1. Known active CNS metastases and/or carcinomatous meningitis. Participants with previously treated brain metastases may participate provided they are radiologically stable, ie, without evidence of progression for at least 4 weeks by repeat imaging (note that the repeat imaging should be performed during study screening), clinically stable and without requirement of steroid treatment for at least 14 days prior to first dose of study treatment.
2. Development of clinically severe non-endocrine autoimmune disorder leading to discontinuation of prior immunotherapy (eg, pneumonitis, myocarditis, neuropathy, or nephritis).
3. Active autoimmune disease that has required systemic treatment in past 2 years (ie, with use of disease modifying agents, corticosteroids or immunosuppressive drugs). Replacement therapy (eg, thyroxine, insulin, or physiologic corticosteroid replacement therapy for adrenal or pituitary insufficiency) is not considered a form of systemic treatment and is allowed.
4. History of solid organ transplant or bone marrow transplant.
5. Myocardial infarction in the 6 months prior to initiating therapy.
6. Class II or greater heart failure per New York Heart Association Classification.
7. Clinically significant bleeding, such as gastrointestinal or intracranial bleeding, or deep vein thrombosis or pulmonary embolism in the 3 months prior to initiating therapy. Thrombus prophylaxis is acceptable.
8. Evidence or clinical suspicion of ongoing serious active infection requiring systemic treatment.
9. Known history of human immunodeficiency virus (HIV) or positive for HIV at screening.
10. Known chronic or active viral hepatitis.
11. Known or suspected severe acute respiratory syndrome coronavirus 2 (SARS-CoV-2) infection, unless patient tests negative for SARS-CoV-2 within the screening period.
12. Parts 3 and 4 only: Has a history of (non-infectious) pneumonitis/interstitial lung disease that required steroids or has current pneumonitis/interstitial lung disease.
13. Parts 3 and 4 only: Has a known additional malignancy that is progressing or has required active treatment within the past 2 years.

Note: Participants with basal cell carcinoma of the skin, squamous cell carcinoma of the skin, or carcinoma in situ (eg, breast carcinoma, cervical cancer in situ) that have undergone potentially curative therapy are not excluded.

Prior/Concomitant Therapy

14. Live or live-attenuated vaccine(s) within 30 days prior to screening or plans to receive such vaccines during the study. Note: Administration of killed vaccines are allowed.
15. Prior chimeric antigen receptor T-cell (CAR-T) or allogeneic cellular therapy.
16. Prior IL-2-based cancer immunotherapy.
17. Diagnosis of immunodeficiency or is receiving ongoing systemic immunosuppressive therapy (stable replacement doses of systemic prednisone ≤ 10 mg/day or equivalent will be allowed) or any other form of immunosuppressive therapy within 7 days prior the first dose of study treatment.
18. History of hypersensitivity to PEG or PEGylated drugs.
19. Parts 3 and 4 only: Has severe hypersensitivity (\geq Grade 3) to pembrolizumab and/or any of its excipients.
20. Parts 3 and 4 only: Patients on a prior PD-1 or PD-L1 inhibitor who experienced a Grade 3 or higher irAEs.
21. Parts 3 and 4 only: Has received prior therapy with an anti-PD-1, anti-PD-L1, or anti PD-L2 agent or with an agent directed to another stimulatory or co-inhibitory T-cell receptor (eg, CTLA-4, OX 40, CD137), and was discontinued from that treatment due to a Grade 3 or higher irAE.
22. Parts 3 and 4 only: Has received prior systemic anti-cancer therapy including investigational agents within 4 weeks (could consider shorter interval for kinase inhibitors or other short half-life drugs) prior to treatment.

Note: Participants must have recovered from all AEs due to previous therapies to \leq Grade 1 or baseline. Participants with \leq Grade 2 neuropathy may be eligible. Participants with endocrine-related AEs Grade ≤ 2 requiring treatment or hormone replacement may be eligible.

Note: If the participant had major surgery, the participant must have recovered adequately from the procedure and/or any complications from the surgery prior to starting study intervention.
23. Parts 3 and 4 only: Has received prior radiotherapy within 2 weeks of start of study treatment. Participants must have recovered from all radiation-related toxicities, not require corticosteroids, and not have had radiation pneumonitis. A 1-week washout is permitted for palliative radiation (≤ 2 weeks of radiotherapy) to non-CNS disease.
24. History of drug-induced Stevens Johnson syndrome, drug reaction with eosinophilia and systemic symptoms (DRESS syndrome) or drug induced toxic epidermal necrolysis.
25. Anticoagulation, unless patient has been on a stable dose of their anticoagulant for ≥ 4 weeks without new thrombotic or clinically significant bleeding events.
26. Concurrent therapy with any other investigational agent, vaccine, or device. Concomitant participation in observational studies is acceptable after Sponsor approval.

Prior/Concurrent Clinical Study Experience

27. Current enrollment or past participation within the last 28 days before first planned dose (Cycle 1 Day 1) in any other clinical study involving an investigational study treatment or any other type of medical research.

Note: Participants who have entered the follow-up phase of an investigational study may participate as long as it has been 4 weeks after the last dose of the previous investigational agent.

Diagnostic Assessments

28. Diabetes mellitus with hemoglobin A1c \geq 8.5% at screening.
29. Corrected QT interval (QTc) > 470 milliseconds or known history of familial long QT syndrome.

Other Exclusions

30. Major surgery in the 8 weeks prior to initiating therapy.
31. Any serious medical condition (including preexisting autoimmune disease or inflammatory disorder), laboratory abnormality, psychiatric condition, or any other significant or unstable concurrent medical illness that in the opinion of the Investigator would preclude protocol adherence or would make the safety of the study drug difficult to assess.

5.3 Screen Failures

Screen failures are defined as patients who consent to participate in the clinical study but do not meet inclusion/exclusion criteria for study treatment. A minimal set of screen failure information is required to ensure transparent reporting of screen failure patients to meet the Consolidated Standards of Reporting Trials (CONSORT) publishing requirements and to respond to queries from regulatory authorities. Minimal information includes demography, screen failure details, eligibility criteria, and any serious adverse event (SAE).

Individuals who do not meet the criteria for participation in this study (screen failure) may be rescreened 1 time. Informed consent is required before patients can be rescreened if outside the original 28-day screening window. See [Section 10.1.3](#) for Informed Consent Process details.

